#### G. Patient Recruitment and Consenting Process

##### Patient Recruitment

A total of 36 patients with short bowel syndrome (SBS)  $\leq$  12 months of age will be recruited for this study. Of the 36 patients, approximately 24 patients will have colon in continuity and 12 will have colon not in continuity. Assuming a 10% dropout rate, it is expected that 32 SBS patients will complete the study.

For Aim 3 of the study, an additional 12 infants without SBS will be enrolled as the non-SBS control patients. Therefore, a total of 48 patients will be enrolled across the two sites, University of Michigan and Cincinnati Children's Hospital Medical Center.

The study will be explained in detail by the study coordinator or other study team member and the consent form will be reviewed per institutional IRB requirements. These subjects will be recruited through the Division of Gastroenterology, Hepatology, and Nutrition, the Department of Surgery, or the Division of Neonatology. The prospective patients will be identified through the clinical staff within all three divisions working collaboratively. The clinical staff will initially inform potential subjects and families about the research study. The research staff will notify and obtain permission from the patient's primary gastroenterologist, surgeon, or neonatologist before contacting the family.

Subjects who drop out prior to drug initiation may be replaced with new subjects until target enrollment is achieved, as these will not have been given study medication.

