## H. Study Procedures

### **Randomization and study groups**

[figure not shown]
At the baseline visit, SBS subjects will be block randomized in a 1:1 scheme by site and strata (i.e the presence or absence of **colon in continuity**) to receive either L-GLN powder or isonitrogenous, isocaloric placebo [L-alanine (ALA)]. Randomization will be done by the Cincinnati Children's Hospital Medical Center research pharmacist who will not be blinded. Distribution will be done by the site study personnel. The subjects, site investigators and study personnel at all sites will be blinded to the randomization. Since patients will be on breast milk or Elemental formula (Elecare® being the preferred elemental formula at both institutions; however use of other elemental formula does not exclude the patient from the study), the randomization process will take into account whether breast milk or formula is been consumed by the infant. The research pharmacist will make decisions regarding randomization based on the use of formula versus breast milk to ensure adequate distribution within groups.

**Glutamine group:** Infants randomized to the GLN group will receive L-GLN administered enterally at a dose of 0.6g/kg body weight/day (0.3g/kg/dose) in 2 divided daily doses for 6 months (figure 2). GLN will be dissolved in water, breast milk or formula and administered to the subject orally or through their enterostomy tube approximately every 12 hours (twice a day). This can be administered as a bolus or a continuous infusion lasting a maximum of 2 hours. We will use Nutrestore™ (Emmaus Medical, Inc.), a commercially available, FDA approved pure L-GLN product in the study. In the event that this is not available we will use commercially available 100% USP grade L-GLN. The minimal volume L-GLN will be dissolved in at least 10 ml of water, breastmilk or formula.

**Placebo group:** Infants in the placebo group will receive ALA at a dose of 0.6g/kg body weight/day in 2 divided doses (0.3g/kg/day twice a day), exactly as outlined above for the GLN group.

ALA is a non-essential amino acid and will be used as the placebo in this study because it is a nutritional supplement without any known impact on gastrointestinal permeability or local effect on the mucosa or infections. It will balance out the administration of an amino acid (L-GLN) to the study population.

Figure 2: Study design

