## **Recording of Adverse Events**

Adverse event recording will begin after administration of study medication.

Diagnostic and therapeutic non-invasive and invasive (i.e. surgical) procedures will not be reported as adverse events. However, the medical condition for which the procedure was performed must be reported if it meets the definition of an adverse event, unless it is pre-existing (prior to initiating GLN).

Medical conditions/diseases present before starting drug are only considered adverse events if they worsen after starting treatment.

Symptoms of the original or targeted disease are not to be considered adverse events in this treatment. The following symptoms are indicative of underlying disease and will not be reported as adverse events: Malabsorption, growth failure, liver disease and BSI.

Abnormal laboratory values or test results constitute adverse events if they induce clinical signs or symptoms or require therapy. They are to be recorded on the Adverse Events CRF under the signs, symptoms or diagnoses associated with them. CA-BSI will only be reported as an adverse effect if the rate is higher than 20% of what is standard for the center.

As far as possible, each adverse event will be assessed by the Investigator with respect to its duration (start and end dates), the severity grade (mild, moderate, severe, life-threatening, fatal), its relationship to the drug (unrelated, unlikely to be related, possibly, probably and definitely related), the action(s) taken, the outcome (i.e. resolved, resolved with sequelae, continuing), gravity (SERIOUS or NOT SERIOUS), and expected/unexpected on the basis of drug insert.

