### **XIII. Statistical Analysis Plan**

To assess the comparability of the two treatment groups, demographic and baseline data will be summarized for each treatment group. For continuous data, mean, standard deviation, median, min, max, first quartile and third quartile will be presented. Comparisons will be made using the two-independent sample t-test or the Wilcoxon Rank sum test, depending on the distribution of the variable. For categorical data, frequencies and percentages in each group will be presented. Comparisons will be made using Fisher's exact test. These tests will be conducted at the two-sided, 5% level of significance. In addition, demographic and baseline data for the control group will be summarized and presented as described above. The statistical analysis plan for each aim is presented below.

**Aim 1 Hypothesis:** Enteral GLN supplementation in infants with SBS after massive bowel resection for NEC will decrease BSI, and thereby decrease systemic proinflammatory cytokine concentrations.

The primary outcome variable is the incidence of BSI during the 6 months on GLN supplementation. BSI is defined as laboratory-confirmed, culture-proven bloodstream infections that meet the Centers for Disease Control and Prevention (CDC) definition. To compare the incidence of BSI during the 6 month time period, the percent of patients with at least one BSI will be calculated in each group. Since this is a pilot study, the desire is to detect a trend in improvement of BSI with GLN supplementation. Therefore the 2 groups will be compared using the Fisher's Exact test at the one-sided 10% level of significance which will indicate a significant trend. As an additional analysis, time to first BSI will be displayed using Kaplan-Meier (K-M) curves. The log-rank test will be used to test for differences in curves between treatment groups. Patients will be censored if they exit the study prior to having their first BSI. As a further exploratory analysis, time to multiple-event analyses techniques will be used to compare groups where the multiple events represent multiple episodes of BSI within patients.

Secondary outcomes include the following and will be tested at the two-sided 5% level of significance:

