- 1) Plasma proinflammatory cytokine levels: TNF- $\alpha$ , IL1- $\beta$ , IL-6, and IL-8. Change from baseline values at 180 days will be computed for cytokine levels. Change from baseline to 180 days values will also be calculated for the flagellin and LPS IgG levels. Appropriate transformations of the data (e.g. log) will be done prior to calculating change from baseline in order to meet the assumptions of the analyses (i.e. normality, equal variance). Analysis of covariance techniques will be used to compare the change from baseline scores of the treatment groups. Covariates included in the analysis will be baseline value, age, gender, ostomy status, feeding type (formula, breast milk).
- 2) Length of hospital stay and number of readmissions: For length of hospital stay, treatment groups will be compared using the Wilcoxon Rank Sum test. For number of readmissions, either a Wilcoxon Rank Sum test or a Chi-Square test for homogeneity will be used to compare groups, depending on the variability of the number of readmissions.
- 3) Stool sIgA levels: Treatment groups will be compared using the random effects repeated measures analysis of covariance. The response variables for each of the parameters will be change from baseline. The time points included in the analyses will be 30, 60, 90, 120, 150, 180 days post-baseline. If required to meet the assumptions of the analyses (normality, equal variances), appropriate transformations will be used. Treatment groups will be compared at each individual time point using appropriate contrasts and the error term from the repeated measures model. Covariates will include baseline value, age, gender, ostomy status, feeding type (formula, breast milk).
- 4) Proportion of nutrition delivered enterally versus parenterally: The statistically analysis approach for this endpoint will be the same as for the Stool sIgA levels discussed above. Transformations appropriate for proportions may be used, if necessary, to meet assumptions of the analyses.
- 5) Plasma glutamine: The statistical analysis approach for this endpoint will be the same as for the proinflammatory cytokine levels discussed above.
- 6) Impact of level of compliance on outcome will be evaluated for a dose effect analysis.

**Aim 2 Hypothesis:** Enteral GLN supplementation will improve somatic growth parameters in Aim 1 patients.

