- 7) The two treatment groups will be compared using the random effects repeated measures analysis of covariance for the following parameters: length velocity, weight velocity, mid arm circumference and head circumference. Length velocity and weight velocity will be analyzed as the post baseline scores. Mid arm circumference and head circumference will be analyzed as change from baseline. The time points included in the analyses will be 30, 60, 90, 120, 150, 180 days post-baseline. If required to meet the assumptions of the analyses (normality, equal variances), appropriate transformations will be used (e.g. log). Treatment groups will be compared at each individual time point using appropriate contrasts and the error term from the repeated measures model. Covariates will include baseline value, age, gender, ostomy status, feeding type (formula, breast milk). For length velocity and weight velocity, the baseline value will be the baseline length and weight values.

To evaluate the impact of BSI on the growth parameters listed above, point biserial correlation coefficients will be constructed overall and within each treatment group and tested to determine significance.

**Aim 3 Hypothesis:** The gut luminal microbiome is altered in pediatric SBS versus non-SBS controls, correlates with BSI and is altered by *enteral* GLN supplementation.

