### **Sample size**

This is a pilot study and will provide estimates of effect sizes and variability to be used to power a future definitive study. The power of this pilot study was investigated based on the primary endpoint of BSI infection rate and the study was powered to detect a trend toward improvement in BSI rates. For this study, we defined “trend” as a significant improvement tested at the one-sided, 10% level of significance. A total of 18 patients per treatment group will be enrolled in the study. Assuming a 10% dropout rate, it is expected that 16 patients per treatment group will complete the study. A sample size of 16 patients per treatment group will provide at least 85% power to detect a trend if the true BSI rates are 75% versus 30% BSI rate at the one-sided 10% level of significance. This calculation is based on the Fisher’s exact test for two proportions.

A sample size of 16 patients per treatment group will also provide at least 80% power to detect a geometric mean ratio of 2.0 for the two treatment groups for the proinflammatory cytokines assuming a coefficient of variation of 0.7 using a two-sided, 5% level of significance test.

We anticipate applying for a follow up R01 /U01 to attract other centers that will allow a larger more definitive study regarding the use of GLN in pediatric SBS.

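### Site, a randomisation factor, is in no efficacy analysis, and colon in continuity enters at best through an undefined ostomy status; adding both is a cheap precision gain if they predict outcome

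*Combined protocol and SAP*

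**What the plan says.** Under Randomization and study groups (section IX.H), "SBS subjects will be block randomized in a 1:1 scheme by site and strata", the strata being colon in continuity or not. Feeding type is also considered at allocation. Patient Recruitment expects that "approximately 24 patients will have colon in continuity and 12 will have colon not in continuity", and the Purpose of Study section plans 18 SBS patients at each of two sites.

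Section XIII analyses the outcomes as follows:

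- **Primary (any BSI):** Fisher's exact test, one-sided 10%, no strata.
- **Time to first BSI:** "The log-rank test will be used to test for differences in curves between treatment groups", no strata and no significance level given for it.
- **Length of stay and readmissions:** rank-sum or chi-square tests, no strata.
- **Cytokines, flagellin and LPS IgG, plasma glutamine:** analysis of covariance. "Covariates included in the analysis will be baseline value, age, gender, ostomy status, feeding type (formula, breast milk".
- **Stool sIgA, share of nutrition given enterally, growth:** repeated-measures models with the same list. For Aim 2: "Covariates will include baseline value, age, gender, ostomy status, feeding type (formula, breast milk".

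Feeding type is the only factor considered at allocation that reaches the models by name. Site appears in none of them, and no section defines ostomy status.

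**The concern.** Blocking within site and colon strata balances those factors across arms, so differences between strata largely drop out of the treatment contrast. A model that omits them still counts that variation as residual error. The reported standard error is then larger than the true one and the test is conservative. The estimate is not biased.

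Two things are at stake. The first is power on the secondary outcomes, which are tested two-sided at 5% with about 32 completers. The second is the pilot's stated product: it "will provide estimates of effect sizes and variability to be used to power a future definitive study". An inflated residual variance would pass into that calculation for continuous outcomes.

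The protocol leaves room for site differences. Growth is measured by each centre's own trained staff on its own equipment, and a nutritionist at each site assesses intake. For infections, "CA-BSI will only be reported as an adverse effect if the rate is higher than 20% of what is standard for the center". Separately, the undefined covariate leaves a coding choice open until after data are seen.

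**Working it through.** **Inputs from the documents.** 18 randomised and 16 completing per arm, cytokine ratio 2.0, coefficient of variation 0.7, two-sided 5% (Sample size); 24 and 12 patients by colon status; 18 per site. Splitting colon status equally across sites, which is an assumption, gives four strata of 12, 12, 6 and 6.

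**The plan's own figures.**

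- Log SD = √ln(1 + 0.7²) = 0.6315. Noncentrality = ln 2 / (0.6315 × √(2/16)) = 0.6931 / 0.2233 = 3.10 on 30 df. Power is 85.2%, consistent with the stated floor of 80%.
- Fisher's test, 75% v 30%, 16 per arm: exact power 85.7%, against at least 85% stated.

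**Residual variance.** Let R² be the share of variance explained by site and colon together, split equally. R² is an assumption.

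- Both missing: ratio about 1/(1 − R²) = 1.11, 1.25, 1.43 at R² = 10%, 20%, 30%. Simulation, which includes the small degrees-of-freedom effect, gives overstatements of 12%, 26% and 45%.
- Site only missing: (1 − R²/2)/(1 − R²) = 0.95/0.90, 0.90/0.80, 0.85/0.70 = 1.06, 1.13, 1.21. Simulation gives 6%, 14% and 23%.

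**Power of the planned five-covariate model at ratio 2.0.** Simulated with stratified 1:1 allocation and 16 per arm, the other covariates taken as non-prognostic.

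| R² | Ostomy = colon: add site | Ostomy unrelated: add site and colon, keep ostomy | Ostomy unrelated: colon replaces ostomy, add site |
|---|---|---|---|
| 10% | 81 → 82% | 79 → 82% | 78 → 82% |
| 20% | 83 → 86% | 79 → 84% | 79 → 86% |
| 30% | 86 → 91% | 80 → 89% | 80 → 91% |

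With R² = 0 the loss is about 1 point at most. Counting only the two lost degrees of freedom (25 to 23), break-even is at R² of about 0.9%. At a ratio of 1.6 and R² of 20%, power rises from 49 to 54% (site added) or from 45 to 53% (both added).

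**Size of the nominal 5% test.** At R² of 10%, 20% and 30%, the planned model rejects in 4.5%, 3.8% and 3.5% of null trials with site missing, and in 3.6%, 3.1% and 2.4% with both missing. The adjusted models stay near 5%. At 20% with both missing, the null estimate's true SD is 0.222 but the mean reported standard error is 0.244; after adjustment both are about 0.218.

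**Log-rank.** Hazard ratio implied by the planned rates = ln 0.70 / ln 0.25 = 0.257. With assumed hazards 3 times higher without colon in continuity and 2 times higher at one site, power is 92% unstratified v 94% stratified by colon (one-sided 10%), or 74% v 78–79% (two-sided 5%). With no stratum effect it is 94.0% v 93.8%, or 80.4% v 79.6%. Stratifying by site as well gained nothing over colon alone in any scenario.

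**Primary test.** A stratified exact test adds 0 to 2 points: 85.9 v 85.9% with no stratum effect, 88.2 v 89.8% with odds ratios of 5 for each factor. Fisher's low actual size (4.4% at a 75% rate, 16 per arm) comes mainly from discreteness.

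**The case against.** The strongest reply is that the gain is small and conditional. If ostomy status is simply the colon stratum, only site is missing and the gain is 1, 3 or 4–5 points. The R² range has no basis in the documents; at 5% the gain is under 1 point. Baseline value is in the models and could absorb stable site differences, which the simulation ignores. A common feeding algorithm and trained measurement staff also limit site variation. All of this stands, and it is why the claim is conditional.

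Further points also stand:

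- The centre-specific BSI standard concerns adverse-event reporting and says little about cytokines or growth.
- The pilot is powered first on a proportion, for which residual variance is not an input.
- A variance estimated on 25 df has a 95% interval of roughly 0.62 to 1.91 times the estimate, wider than the overstatement.
- The repeated-measures growth models were not simulated; the figures come from a single-timepoint model.
- The log-rank gain is marginal and the analysis is supportive.

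None of this answers the gap itself. Site is missing from every efficacy analysis, one listed covariate has no definition, and the possible loss from adding the factors is smaller than the possible gain.

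**Conclusion.** The concern holds. The plan randomises by two factors, analyses neither by name, and uses an undefined covariate that may or may not stand for one of them.

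If site and colon together explain 10% to 30% of the variance, the planned cytokine-type model gives up about 1 to 5 points of power when ostomy status is the colon stratum, and about 3 to 9 points when the two are unrelated and both factors are added. Residual variance is overstated by 6% to 23% or by 12% to 45% respectively. If the factors do not predict outcome, nothing is gained. Carrying the direction of the effect over to the growth models is inference, not calculation.

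There is no threat to validity: no bias, no excess false positives, and no reason to change the primary test. This is a worthwhile improvement at very low cost, with medium confidence because prognostic strength is unknown.

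**What to change.** - Define ostomy status and state how it relates to the colon-in-continuity stratum.
- Add site and colon in continuity, as randomised, to every analysis of covariance and repeated-measures model. Let colon replace ostomy status if the two coincide or degrees of freedom are short.
- Stratify the supportive log-rank test by colon in continuity, and state its significance level. Add site only if the four strata are not sparse.
- Leave the primary Fisher test as planned.

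The cost is SAP wording and one degree of freedom (site) or two (both). Both factors are known at randomisation, so no new data are needed. If they prove non-prognostic, the loss is about 1 power point at most in the covariate models, under 1 point for a log-rank test stratified by colon, and 1 to 2.5 points if it is stratified by both.

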#### F. Evaluating compliance

All of the subjects will be instructed to bring to the monthly visits, the containers containing the supplement supplied at the previous visit. The study team will count the remaining bags left over. We will also evaluate the diary provided to the families. Compliance will be evaluated based on the diary and the number of returned containers. Families are expected to be 90% compliant. If the child/family is less than 90% compliant, the family will receive additional counseling to identify reasons and how to attain this level of compliance. Children will remain in the study as long as they receive at least 70% of the expected amount for 3 consecutive months. The level of compliance on enteral GLN effect will be included in the analysis. Children who receive less than 70% or more than 120% of the prescribed glutamine or placebo will be considered to be non-compliant. The reason for non-compliance will be documented and included in the final analysis. Average intake/day of glutamine by the patients will be included in the analysis including the response based on dose received.

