4. The family will be instructed on how to administer GLN and placebo. During the baseline visit, the initial teaching will be done and they will be provided with the premeasured powder. The dose (0.6g/kg/d (0.3g/kg/dose) of GLN or ALA) will be measured out in the research pharmacy based on the weight of the child at the visit into individual packets. Children hospitalized during the study will receive GLN or ALA from the research pharmacy delivered to the patient's bedside to be administered by nursing staff. At subsequent visits (except visit on day 180), this teaching will be repeated as the dose to be administered will change based on the weight of the child. The family will also be given a weekly drug diary to complete in between visits. They will return the drug diary to the study staff during subsequent visits.
5. During the initial visit, stool will be collected into sterile containers and stored at -80°F until analysis for sIgA and bacterial composition evaluation. It is anticipated that the majority of stool will be collected in clinic during the study visit. If stool is collected in clinic, the stool will be stored immediately in the -80°F freezer without any need for DNA stabilizer.

If stool is not collected during this visit, families will be instructed on how to collect stool for evaluation into a sterile container. They will put this in a storage bag and kept cold until picked up by the home health team or delivered to the research team.

Patients already enrolled will be provided with a sterile container with instructions to collect stool and bring in to the clinic visit for storage and analysis. The family will be asked to collect stool 24-48 hours before their clinic visit and put the stool in a sterile container which will be supplied to them by the study team. They will put this in a storage bag and keep cold. They will bring the sample to the clinic visit. RNAlater may be used with samples when samples are unable to be obtained within 24 hours of the clinic visit.

**Stool sIgA analysis:** sIgA will be determined by ELISA as described.

**During baseline visit and visit on day 180** the following additional procedures will be done: Extra 2 ml of blood will be collected for plasma glutamine, proinflammatory cytokines analysis, flagellin and LPS specific IgG levels.

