**During a BSI** the following procedure will be done: stool collection for bacterial analysis and sIgA measurement. Extra 2 ml of blood will be collected for flagellin and LPS specific IgG levels. The blood will be obtained as soon as possible when the patient is being investigated for a suspected CA-BSI. In the event that the episode does not meet the criteria for a CA-BSI the samples will not be evaluated.

All bacterial isolates obtained during the study from patients will be saved at their respective institutions (CCHMC and University of Michigan) until the end of the study in the event further work with them is required.

**Plasma glutamine analysis:** Plasma GLN will be performed using quantitative ion exchange chromatography.

**Proinflammatory cytokine evaluation:** Analysis will be performed utilizing Luminex xMAP technology (Austin TX) as previously described.

**Measurement of Flagellin and Lipopolysaccharide- specific Immunoglobulin G level:** This will be done using enzyme-linked immunosorbent assay (ELISA) as previously described.

**Safety evaluation:** The study coordinator will contact the family by phone to assess for the development of any serious adverse events on days 15(±7 days), 45 (±7 days), 75 (±7 days), 105 (±7 days), 135 (±7 days) and 165 (±7 days). There will be a 7 day grace period before and after the desired date of safety evaluation phone calls. The phone interview will assess safety and evaluate for any symptoms suggestive of adverse side effects related to L-GLN. If hospitalized, the safety evaluation will occur with the primary caregiver (bedside nurse or parent).

**Additional safety precautions:** If while enrolled in the study the patient develops multiorgan failure or requires vasopressors, the study drug will not be administered.

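### The dose-effect analysis does not limit intake to time before the event, so doses lost or unrecorded because of a BSI can create a false protective dose-response

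*Combined protocol and SAP*

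**What the plan says.** The dose-effect analysis is item 6 among the Aim 1 secondary outcomes in section XIII, which are tested at the two-sided 5% level: "Impact of level of compliance on outcome will be evaluated for a dose effect analysis". Section IX.F (Evaluating compliance) names the exposure: "Average intake/day of glutamine by the patients will be included in the analysis including the response based on dose received". It also says how intake is measured: "Compliance will be evaluated based on the diary and the number of returned containers". The target there is stated as "Families are expected to be 90% compliant", and the limits as "Children who receive less than 70% or more than 120% of the prescribed glutamine or placebo will be considered to be non-compliant".

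Two statements in section IX.H bear on how a BSI can change intake. Under additional safety precautions: "If while enrolled in the study the patient develops multiorgan failure or requires vasopressors, the study drug will not be administered". Under the visit procedures: "Children hospitalized during the study will receive GLN or ALA from the research pharmacy", given at the bedside by nursing staff.

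No section states the averaging period, the denominator, which outcome is meant, which arm or arms are used, the model, or the order in time of intake and outcome.

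**The concern.** A dose-response analysis needs exposure to precede outcome. BSI is the Aim 1 primary outcome, so it is the natural candidate for the outcome in item 6, and an average over follow-up is the natural reading of average intake per day. On that reading, intake after a BSI helps to explain that same BSI.

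The documents give two routes from a BSI to lower intake. The first is actual: drug is not given in multiorgan failure or during vasopressor use, and either can follow sepsis. The second is in the record: compliance comes from the family's diary and returned containers, while inpatient doses come separately from the research pharmacy. Unless inpatient doses are added, unused home packets could count as missed doses for an infant who was in fact dosed.

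Randomization does not protect a comparison by dose received within an arm. The protocol lists suboptimal dose among possible reasons for earlier inconsistent results (sections II and III) and says the data will inform Phase III studies. A false finding that more glutamine means fewer BSIs would fit that expectation and could be carried forward.

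**Working it through.** **The plan's own figure.** The documents give no figure for the dose-effect analysis. The stated power of the primary test does reproduce: Fisher's exact test, 16 per arm, 75% v 30%, one-sided 10%, gives 85.7% by exact enumeration (stated: at least 85%). That test compares randomized groups and does not use intake.

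**How common BSI is.** Section III cites 7.8 catheter sepsis episodes per 1000 catheter days in short bowel syndrome. Over 180 days this is 0.0078 × 180 = 1.404 expected episodes, and P(at least one) = 1 − exp(−1.404) = 75.4%, in line with the 75% in the sample size section.

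**Expected shift in average intake with no glutamine effect.** Infants with any BSI average 1.404 / 0.754 = 1.86 episodes. With mean compliance of 92% (assumed) and d days lost per affected BSI, their average intake falls by 1.86 × d / 180 × 92 points:
- d = 3: 2.9 points
- d = 7: 6.7 points
- d = 14: 13.3 points
- d = 7 but only 30% of BSIs affected: 2.0 points

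**False positives.** Average 180-day intake in infants with and without BSI was compared by a two-sided Wilcoxon test at 5%, simulating no effect of intake on BSI. Days lost, share of BSIs affected and between-infant SD are assumptions. One arm of 16 fits the reference to glutamine intake; 32 is both arms.

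Setting A: mean compliance 90% (the target in IX.F), 30% or 75% of infants with BSI, SD 5 or 10 points, every BSI affected.

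| Days lost per BSI | n = 16 | n = 32 |
|---|---|---|
| 0 | 3.3-3.5% | 3.9-5.2% |
| 3 | 4.4-10.5% | 7.2-19.2% |
| 7 | 8.5-34.5% | 19.6-67.1% |
| 14 | 24.7-74.1% | 57.9-97.5% |

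Setting B: 7.8 per 1000 days, mean compliance 92%, SD 5 to 15 points, share of BSIs affected varied.

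| Share affected, days lost | n = 16 | n = 32 |
|---|---|---|
| 100%, 7 days | 8-37% | 17-76% |
| 30%, 14 days | 5-11% | 10-29% |
| 30%, 7 days | about 5% | 6-13% |
| 10%, 3-14 days | 3-5% | 5-7% |

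**Check of the remedy.** In setting A, intake on days 0-29 was compared with later BSI in infants BSI-free at day 30. The rejection rate was 3.1-5.0% and the intake difference was within 0.3 points of zero in every case.

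**The case against.** A reader might infer that the plan averages intake over all study days, relates it to BSI, and so will report a false dose-response. The documents do not support that. The window and the outcome are unstated. Withholding is documented only for multiorgan failure and vasopressor use, not for every BSI. Dosing otherwise continues in hospital under nursing supervision, which could keep intake at or above the home level. Multiorgan failure is also an exclusion criterion, and developing one is a withdrawal criterion, so some of these infants would leave the study rather than accumulate withheld days.

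The large percentages also need a week or more lost at every BSI. IX.F provides for intake below 70% and above 120%, which suggests a wide spread of compliance, and a wide spread dilutes the bias: with SD 15, n = 16 and every BSI affected, false positives are about 5%, 10% and 23% at 3, 7 and 14 days.

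All of this stands and makes the size conditional. It does not remove the problem. Continued inpatient dosing helps only if those doses enter the intake record, and the plan does not say that they do. For withdrawn infants the effect depends on the unstated denominator.

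**Conclusion.** The concern holds in conditional form. As written, the analysis allows intake after a BSI to count as exposure for that BSI, and the documents contain both an actual and a recording route by which a BSI can lower intake. If BSI is the outcome and intake is averaged over follow-up, a false protective association can arise without any glutamine effect.

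Its size cannot be fixed from the documents. It is about nominal if few BSIs are affected, or if about 3 days are lost with a wide spread of compliance. It is roughly 8-37% (n = 16) or 17-76% (n = 32) if every BSI costs 7 days, and higher at 14 days. These ranges rest on assumed days lost, share of BSIs affected and compliance SD.

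The damage is confined to item 6. The primary Fisher test, the log-rank comparison and the stated power rest on randomized groups and are unaffected.

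**What to change.** Change the SAP wording for item 6 and section IX.F as follows:

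- For BSI, use only intake before the first BSI. Either use a landmark (for example, day 0-29 intake against later BSI in infants BSI-free at day 30) or enter lagged intake in the time-to-first-BSI analysis.
- Count inpatient doses in the intake record, and state the denominator, including how withheld days and days after withdrawal are treated.
- Run the same analysis of alanine intake in the placebo arm as a negative control. A similar slope there would point to bias rather than a glutamine effect.
- Label the result observational and exploratory.
- Do not adjust the dose-response for growth or cytokines for the number of BSIs. The Aim 1 hypothesis makes BSI the mediator for cytokines, and Aim 2 examines its impact on growth, so adjustment could remove a real effect.

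No new data collection is planned for: weekly drug diaries and BSI dates are already collected, and inpatient doses are dispensed by the research pharmacy. The cost is information. At 7.8 per 1000 days, exp(−0.0078 × 30) = 79% of infants are BSI-free at day 30, about 12.7 of 16 per arm. Infants with an early BSI contribute little or no exposure data, and estimates from 16 infants per arm will be imprecise.
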